- Rather, a *randomized encouragement design* is adopted in which respondents in randomly selected barangays will be offered the opportunity to enter a lottery for a money prize on condition of attending a RHU/CHC for a checkup within a month. The lottery will have a selection probability of 10% and a prize of 5,000 PHP. There will be one lottery within each of the selected barangays.

- The offer of a lottery ticket will be used to instrument presentation for checkup at RHU/CHC allowing the effect of the latter on predicted 10-year CVD risk, plus risk factors (smoking, BMI, blood pressure), hypertension diagnosis and medication at follow-up to be identified.
- Specifically, we will estimate the regression model,

$$Y_{it} = \gamma Y_{it-1} + \beta x_{it-1} + \tau \,\hat{s_i} + \mu_{it} \tag{6.1}$$

where Y_{it} represents the outcome variable (e.g. predicted CVD risk) at follow-up and \hat{s}_i is the predicted value of a binary variable that equals one for those who attended a RHU/CHC for a checkup, and zero otherwise. The prediction is obtained from the first stage regression described in [H6b] that makes use of the random offer of entry to the lottery. Y_{it-1} and x_{it-1} are the outcome and covariates respectively at baseline. Note that only individuals that are either in the lottery incentive group or in the control group are used for this regression.

• The instrumental variable estimate of τ is an estimate of the impact of a RHU/CHC checkup on the outcome for those induced to present for checkup by the lottery offer who would not have presented for a checkup otherwise.

[H6b] The lottery offer is a strong instrument for presentation at a RHU/CHC for a checkup.

Test:

• Using both the treated respondents who are offered the lottery prize and the control respondents who are not, we will regress a binary variable indicating RHU/CHC attendance (s_i) on a binary variable indicating whether or not the lottery prize was offered (L_i) , i.e.

$$s_i = \gamma Y_{it-1} + \beta x_{it-1} + \kappa L_i + u_i.$$
(6.2)

 $\hat{\kappa} > 0$ indicates that the lottery offer raises attendance. We will test for weakness of the instrument.

[H6c] Individuals who have a preference for risk respond more to the offer of a lottery prize. Thus, the intervention has a larger effect on individuals who potentially engage most in lifestyles that bring exposure to CVD risk.

Elaboration

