We will use Prospect Theory (Kahneman and Tversky 1979; Tversky and Kahneman, 1992) to examine how response to the lottery varies with a richer characterization of risk attitudes captured by a value function, u(x), and a probability weighting function, w(p), that maps probabilities to decision weights. Prospects are valued as $PT(x_p y) = w(p)u(x) + (1-w(p))u(y)$. We intend to assume power utility $u(x) = x^r$ where r indicates the curvature of the value function for gains. We plan to use the oneparameter form of the probability weighting function introduced by Prelec (1998), $w(p) = \exp(-(-\ln p)^{\alpha})$. When the *likelihood insensitivity* parameter is less than one, < 1, there is overweighting of small probabilities and underweighting of moderate and large probabilities. Under $\alpha > 1$ the weighting of small probabilities and large probabilities is reversed. With $\alpha = 1$ all probabilities are weighted linearly. For given α , smaller r corresponds to more risk averse behaviour.

In this framework, the demand for preventive care and the impact of the lottery on that demand depends on the parameters r and a, as well as the probability of winning the lottery in relation to the perceived CVD risk. Consider an individual with a < 1. Over a large range of p (approximately 15-80%), w'(p) < 1and demand for preventive care is suppressed because the individual perceives that it would have little impact on the probability of having a heart attack or stroke. This individual also over weights the probability of winning the lottery. Hence, she will react strongly to the lottery. An individual with a < 1who perceives the CVD risk to be lower, say 5%, may have w'(p) > 1 – she perceives that prevention has a large impact on the CVD risk. Hence, without the lottery, her investment in preventive care will be higher than the first individual and, although the lottery remains attractive because of over weighting the probability of winning, its impact on preventive care must be lower than for the first individual.

By utilizing individual-specific estimates of r, a and perceived CVD risk, we can therefore form categories of individuals we expect to respond more and less to the lottery.

Test:

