- The likelihood insensitivity parameter, α_i , and the utility curvature parameter, r_i , will be identified for each individual *i* using their responses to hypothetical lottery (in gain domain) choice questions specifically designed for use in a survey context and previously used in the Philippines to estimate risk preferences (Van Wilgenburg et al., 2017).
- First, we will test whether compliance varies with a composite measure of risk aversion that comprises both utility curvature and likelihood insensitivity. Using r_i and α_i we will compute

each individual's certainty equivalent of the lottery (CE_i) , and subtract this from the expected value of the lottery (EV = 500) to get the risk premium R_i . This is calculated for all individuals irrespective of whether they are in the treatment group offered the lottery. $R_i > 0$ indicates risk aversion, $R_i < 0$ indicates risk loving and $R_i = 0$ is risk neutrality.

• We will estimate the following regression model,

$$s_i = \gamma Y_{it-1} + \beta x_{it-1} + \psi_1 L_i + \psi_2 R_i + \psi_3 L_i \times R_i + u_i.$$
(6.3)

- ψ_1 corresponds to the lottery response of risk neutral individuals.⁴ This will be positive if the expected gain from the lottery (500 PHP) is sufficient to bridge the shortfall of the expected health gain of the checkup from its cost. In the absence of the lottery incentive, this shortfall presumably explains why the individual does not go for a checkup. If the estimate of this parameter is not significantly greater than zero, we will learn that the perceived gains of a checkup fall short of the costs by more than 500 PHP.
- $\psi_3 < 0$ corresponds to greater compliance among more risk loving individuals.
- Because the estimates of the individual specific risk parameters, and so the risk premium, can be expected to be noisy, we will also try an alternative specification that enters binary indicators of whether the respondent is risk loving or risk averse (interacted with the lottery indicator) into the first stage regression, with risk neutral being the reference category.
- After having established whether compliance varies with a composite measure of risk attitudes, we will explore whether response to the incentive varies with utility curvature and likelihood insensitivity separately. We will estimate the following type of regression model,

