$$s_{i} = \gamma Y_{it-1} + \beta x_{it-1} + \phi_{1} L_{i} + \phi_{2}(r_{i}-1) + \phi_{3} 1(\alpha_{i} < 1) + \phi_{4} L_{i} \times (r_{i}-1) + \phi_{5} L_{i} \times 1(\alpha_{i} < 1) + u_{i}$$

$$(6.4)$$

- ϕ_1 is the response to the lottery of individuals with linear utility who do not overweight small probabilities.
- $\phi_4 > 0$ indicates greater compliance from those with a less concave utility function. Conditional on the likelihood insensitivity parameter, this implies greater response from less risk averse individuals, which is what we expect.
- $\phi_5 > 0$ indicates greater compliance of those who overweight small probabilities, which is expected if one considers only the overweighting of the probability of winning the lottery and ignores the consequence of the likelihood insensitivity parameter for the demand for preventive care without the lottery incentive.
- Because of the anticipated noise in the estimates of the risk parameters, we will consider alternative specifications that do not enter the utility curvature parameter estimate (r_i) continuously, but group the respondents by whether this estimate is less than, equal to or greater than 1.
- Finally, we will classify individuals into groups according to values of the risk parameters and CVD risk perceptions and compare response to the lottery across these groups. For example, compliance is likely to be high among individuals with convex utility who overweight small

⁴ We include the baseline values of the outcome and the covariates in this regression to maintain its interpretation as the first stage of an IV model. However, to explore variation in response to the randomly assigned lottery, these controls should not be necessary.

probabilities and perceive the CVD risk to lie in the range in which it is believed to be affected little by prevention ($r_i > 1$, $\alpha_i < 1$, 0.15).

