• To characterize the risk preferences of compliers, we will run the first stage regression (6.2) separately for individuals with $R_i > 0$, $R_i = 0$ and $R_i < 0$ and compute the relative likelihood that a complier is risk averse/risk neutral/risk loving, which is given by the ratio of the estimated response to the lottery in the respective group to the response in the full sample. A higher relative likelihood for the $R_i < 0$ group supports our hypothesis that a complier is more likely to be someone with a preference for risk. We will follow the same procedure for groups formed from different combinations of α_i and r_i in order to test, for example, whether a complier is more likely to have convex utility and overweight small probabilities.

[H6d] Individuals who are impatient and who display a present bias respond more to the lottery offer. Thus, the intervention has a larger effect on individuals who engage most in risky lifestyles that offer immediate reward and invest least in preventive health behavior that gives a long-run gain for a short-run cost.

Elaboration

Benefits from preventive care and health behaviour are derived in the long run. Individuals who discount the future more are expected to invest less in prevention and indulge more in lifestyles that yield immediate benefits but carry long-term health risks. Conversely, those who discount less aggressively are more likely to be always takers of preventive care and healthy behaviours.

The chance to win a lottery brings the benefits from preventive care forward, which is valued most by the least patient individuals. Hence, these subjects are more likely to respond to the lottery offer.

Investment in preventive care can be further discouraged by present bias – the tendency to place additional weight on costs and benefits experienced immediately resulting in a discount rate over a length of time that is higher when the period begin in the present. Such bias can result in failure to implement plans for healthier living. From a distance, diet or exercise in the future can seem desirable but when the time comes to start dieting or exercising the immediate costs outweigh the heavily discounted long-term gains.

The opportunity to enter a lottery conditional on going for a checkup at a RHU/CHC gives the respondent the chance of a more immediate reward for the cost of taking this preventive action. Hence, it may help counter present bias.

Test:

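### H6c's secondary groupings use a 15% lower limit that the plan's own weighting function does not give, and exact-equality neutral groups with no stated tolerance

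*Combined protocol and SAP*

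**What the plan says.** Section 3.2 of the combined protocol and SAP, under [H6c], sets out a prospect-theory account of who responds to the lottery. The utility assumption is introduced with "We intend to assume power utility", u(x) = x^r. Probabilities are weighted by the one-parameter "form of the probability weighting function introduced by Prelec (1998"), w(p) = exp(-(-ln p)^alpha). For a person with alpha < 1, the Elaboration gives the region where w'(p) < 1, and prevention therefore seems to do little, in these terms: "Over a large range of p (approximately 15-80"%). A person perceiving a 5% risk is the contrast case and may have w'(p) > 1. The last grouping under Test gives as an example people with r > 1, alpha < 1 and a perceived risk in the range thought to respond little to prevention, with 0.15 shown as a bound.

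The risk premium R is the "expected value of the lottery (EV = 500") minus the certainty equivalent. Risk neutrality is R = 0, with no tolerance. Because the individual estimates are expected to be noisy, an alternative model replaces R by risk-loving and risk-averse indicators, "with risk neutral being the reference category". For curvature, another alternative would "group the respondents by whether this estimate is less than, equal to or greater than 1". The complier characterisation runs the first stage (6.2) separately for R above, equal to and below zero.

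**The concern.** Both cut-points should follow from the functions the plan adopts. If the 15% limit is too high, respondents whom the plan's own theory expects to respond strongly are left out of the group formed to show that response, and the comparison between groups is blurred.

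The equality rules raise a different problem. R is computed from two estimated parameters, and an exact zero is a knife-edge. If nobody sits on it, the indicator model loses its named reference and one of the three complier subgroups has no data. Grouping was brought in to deal with noise, and exact equality is the kind of cut that noise disturbs most. If the rule is left open, it may be settled after results are visible.

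**Working it through.** **Inputs.** From Section 3.2: w(p) = exp(-(-ln p)^alpha); u(x) = x^r; "The lottery will have a selection probability of 10% and a prize of 5,000 PHP". From Table 6: lottery 1,361 and control 1,361 for binary outcomes, so 1,361 + 1,361 = 2,722 respondents for H6c. The plan's expected value reproduces: 0.10 × 5,000 = 500 PHP.

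**1. Where w'(p) < 1.** Differentiating, w'(p) = alpha × (-ln p)^(alpha-1) × w(p) / p. Solving w'(p) = 1:

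| alpha | lower crossing | upper crossing | w' at 5% | w' at 15% |
|---|---|---|---|---|
| 0.5 | 5.2% | 85.6% | 1.02 | 0.61 |
| 0.65 | 7.0% | 82.7% | 1.15 | 0.76 |
| 0.8 | 8.6% | 80.1% | 1.16 | 0.88 |
| 0.9 | 9.7% | 78.6% | 1.10 | 0.95 |
| limit 1 | 10.65% | 77.2% | – | – |

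Example at alpha 0.8 and p = 0.15: -ln p = 1.897; 1.897^(-0.2) = 0.880; w = exp(-1.897^0.8) = 0.188; so w' = 0.8 × 0.880 × 0.188 / 0.15 = 0.88.

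As alpha approaches 1, x = -ln p satisfies (x - 1) ln x = 1. The larger root is x = 2.240, so p = exp(-2.240) = 10.65%. The lower crossing rises with alpha, so 10.65% is its ceiling. The plan's upper limit of about 80% is reproduced, and so is its 5% contrast case for alpha of about 0.5 or more. The 15% lower limit is not reproduced at any alpha < 1.

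**2. Where R = 0.** The certainty equivalent is 5,000 × w(0.1)^(1/r) = 5,000 × exp(-(ln 10)^alpha / r). Setting it to 500 gives r = (ln 10)^(alpha-1), a single curve: r = 0.659 at alpha 0.5, 0.747 at 0.65, 0.846 at 0.8 and 1 at alpha 1. With continuous estimates the expected number with R = 0 or r = 1 is zero.

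The documents do not state the estimator or the values r and alpha can take. The table therefore rests on assumed normal spreads: SD 0.3 for r and 0.25 for alpha, with means 0.9 and 0.7, or 1 and 1.

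| How r and alpha are recorded | share with r = 1 | share with R = 0 |
|---|---|---|
| continuous | 0 | 0 |
| grid of mid-points omitting 1 | 0 | 0 |
| grid containing 1, step 0.1 | 13% | 1–2% |
| grid containing 1, step 0.25 | 31–32% | 6–12% |
| grid containing 1, step 0.5 | 57–60% | 23–41% |

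In the continuous case with means 0.9 and 0.7, about 4 of 2,722 have |R| ≤ 1 PHP and about 207 have |R| ≤ 50 PHP.

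**3. If the R = 0 group is empty.** The risk-loving and risk-averse indicators sum to 1, and their interactions with L sum to L. One of each pair is redundant, and the first stage for R = 0 has no observations.

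**The case against.** **The 15–80% statement can be read as a safe sub-range.** The largest w' on that interval is 0.82 at alpha 0.5, 0.94 at 0.65, 0.999 at 0.8 and 1.009 at 0.9, so the sentence is true for alpha up to 0.8 and within 1% above that. The plan also writes approximately, and never says w' > 1 between 5% and 15%. This stands as a defence of the sentence. It does not defend 0.15 as a group boundary, since people below it can meet the same condition.

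**The example may intend something stricter than w' < 1.** It speaks of risk affected little by prevention, and at a risk of 11.35% w' is 0.94 (alpha 0.8) or 0.98 (alpha 0.9). That is fair for alpha near 1. It is weaker at alpha 0.5, where w' at 11.35% is already 0.68. The group is also only an example, and its inequality is incomplete in the text available, so no binding 0.15 rule can be read from it.

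**A reader might infer that many respondents are misplaced, because the assumed mean risk of 11.35% (Section 10.1) lies below 15%.** The documents do not support this. That figure is a Globorisk-predicted mean, whereas the grouping uses perceived risk, and Section 7 says the information for power calculations on perceived-risk outcomes is lacking.

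**A reader might also infer that the neutral reference group will be empty or nearly so.** That is not established. The parameters come from survey choice questions, and a coarse grid containing 1 could give a usable group. An empty reference would also do limited harm: the model collapses to risk loving versus risk averse, which is the contrast H6c is about.

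**Conclusion.** The point holds and is minor. Under the plan's own function the lower limit of w'(p) < 1 is about 5% to 10.6% for alpha of 0.5 or more, and never above about 10.65%. A 15% cut leaves out some people who meet the stated rationale, in a number that cannot be given. This result needs no assumption beyond the one-parameter Prelec form.

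The equality groups are empty if r and alpha are continuous or on a grid omitting 1. Under the assumed spreads, R = 0 could instead hold about two-fifths of the sample on a coarse grid. The defect is therefore an unspecified rule, not a demonstrated failure.

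Only H6c's alternative specifications, the example grouping and the complier characterisation are touched. Model (6.3) enters R continuously, (6.4) enters r - 1 continuously and splits alpha only at < 1, and the principal outcome does not depend on any of these groups.

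**What to change.** 1. Replace the 0.15 cut by w'(p) < 1, computed from each respondent's alpha and perceived CVD risk. If noise in the individual alphas is a worry, use a fixed lower cut of about 0.107, which is at or above the lower crossing for every alpha < 1. The fixed cut still leaves out people between their own crossing and 10.7%.
2. State how r and alpha are estimated and which values they can take.
3. Before follow-up data are seen, define neutrality by one band on R and derive the r band from it, or use two groups (R > 0 and R < 0) or quantiles of R. Two bands chosen separately can conflict. With alpha = 1 and r = 0.9, R = 500 - 5,000 × 0.1^(1/0.9) = +113 PHP, so this person would be linear under |r - 1| ≤ 0.1 but not neutral under |R| ≤ 50. At alpha = 1, |R| ≤ 50 corresponds to r from 0.956 to 1.043.

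The cost is SAP wording only, with no new data. The width of a band is a convention, so results should be repeated with a narrower and a wider one, for example ±25 and ±100 PHP around a ±50 PHP choice.

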• We will characterize respondents according to their degree of impatience and whether they display present bias by implementing an instrument used by Ashraf et al (2005) to examine how these traits influence the response to the offer of a savings product in the Philippines. This involves a standard procedure of asking respondents hypothetical questions about whether they would choose to receive a smaller amount of money now or a larger amount in one month. By varying the amount of money offered in one month, respondents who discount more aggressively can be distinguished.

- To identify present bias, respondents are asked to choose between receiving a smaller amount in six months or a larger amount in seven months. Those who choose the smaller amount now rather than the larger amount in one month but who are prepared to wait seven months for the larger amount rather than accept the smaller amount in six months display present bias, or hyperbolic discounting. Those who choose the larger amount in one month rather than the smaller amount now, but who choose the smaller amount in six months rather than the smaller amount now, but who choose the smaller amount in six months rather than the larger amount in seven months also display time inconsistency. We will examine whether response to the lottery differs in this group but since noise is likely to be largely responsible for this type of inconsistency, we do not expect systematic variation in the response of this group relative to others.
- Using these stated choices, we will form groups of respondents who are more/less impatient and who do or do not display present bias.
- In the first stage regression, analogous to the procedure described in [H6c], we will interact the lottery instrument with indicators of the degree of impatience and with an indicator of whether the respondent displays present bias.
- We will then compute and compare the relative likelihoods that a complier is present-biased and impatient to varying degrees.

[H6e] Individuals who underweight small probabilities experience a higher reduction in risk factor exposure and increase in medication through PhilPEN than individuals who weight probabilities linearly and individuals who overweight small probabilities.

Elaboration

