Individuals who underweight small probabilities are less likely to invest in preventive care and to adopt healthier behaviour in response to CVD risks of 10% or so that are significant in terms of potential health impact but are considered small in characterizations of the distribution of probability weights. These individuals are thus likely to be in greater need for preventive interventions and may benefit most from the medication and counselling delivered by PhilPEN.

Test:

• We will run the instrumental variable regression $Y_{it} = \gamma Y_{it-1} + \beta x_{it-1} + \tau \hat{s_i} + \mu_{it}$ as described in [H6a] separately for individuals with $\alpha_i > 1$ and individuals with $\alpha_i \le 1$. A significantly larger $\hat{\tau}$ for individuals with $\alpha_i > 1$ supports the hypothesis.

4. Elicitation of risk perceptions

Elicitation of subjective probabilities of future cardiovascular events is a key input to our analysis of the role of CVD risk perceptions in determining health behaviour and demand for primary prevention. Although the collection of expectations data is complicated by the limited formal education and numeracy skills of most of our sample, there is accumulating evidence that, if questionnaires are carefully designed, the measurement of such beliefs in the developing world is both feasible and valuable (Attanasio, 2009; Delavande et al., 2011a).

Asking respondents directly for probabilities or percent chances is often considered too abstract for developing country settings. Visual aids are commonly used (Attanasio, 2009). For example, the respondent can be asked to allocate physical objects, like beans or stones, representing probability units into a number of bins (Delavande et al., 2011b). Hill (2009) asks coffee farmers in Uganda to distribute 20 beans across three piles representing different price categories in accordance with their predictions of

future coffee prices. Attanasio et al. (2005) ask respondents to indicate a point on a ruler graded from 0 to 100 that corresponds to the likelihood of receiving income in excess of a certain amount.

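### In H6c a higher point estimate of the complier ratio counts as support, with no interval and no named comparator, so chance alone gives nominal support about half the time

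*Combined protocol and SAP*

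**What the plan says.** All references are to section 3.2, Hypotheses and tests, of the combined protocol and SAP.

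- **Complier ratio.** The last bullet of the [H6c] test runs first-stage regression (6.2) separately for R > 0 (risk averse), R = 0 (neutral) and R < 0 (risk loving). The relative likelihood that a complier belongs to a group is "the ratio of the estimated response to the lottery in the respective group to the response in the full sample". A higher value for R < 0 "supports our hypothesis that a complier is more likely to be someone with a preference for risk".
- **Extension to parameter groups.** "We will follow the same procedure for groups formed from different combinations of" α and r, "in order to test, for example, whether a complier is more likely to have convex utility and overweight small probabilities".
- **Interaction models.** Earlier in [H6c]: "First, we will test whether compliance varies with a composite measure of risk aversion that comprises both utility curvature and likelihood insensitivity". This is model (6.3), where a negative coefficient on lottery × R "corresponds to greater compliance among more risk loving individuals". An alternative specification interacts the lottery with risk-loving and risk-averse indicators, with risk neutral as reference. Model (6.4) interacts the lottery with r and with an indicator for α < 1, each separately.
- **[H6d].** After lottery-by-preference interactions: "We will then compute and compare the relative likelihoods that a complier is present-biased and impatient to varying degrees".
- **Contrast, [H6e].** "A significantly larger" τ estimate in the subgroup that underweights small probabilities is what supports that hypothesis.

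The 5% significance level appears in section 10.1, for the power calculation, and is not tied to the ratio.

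**The concern.** The ratio is an estimate, but its reading is a bare comparison: higher or not. The bullet gives no measure of uncertainty and does not say what the ratio must be higher than. Three comparators are possible: 1 (the full sample), the risk-averse group, or both other groups. A comparison of two estimates with the same expectation goes either way about equally often, so such a rule has no useful control of false support.

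What is at stake is the account of who the compliers are. The lottery analysis estimates a local effect for people moved to attend by the offer, and [H6c] argues that they tend to prefer risk and may live less healthily. A profile that could be chance might be reported as confirming that account, even if the interaction in (6.3) showed nothing, because the plan does not say which prevails.

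**Working it through.** **1. The plan's own sample size.** Inputs from section 10.1: 5% significance (taken as two-sided), 80% power, effect 0.2 SD diluted by 60% compliance to 0.2 × 0.6 = 0.12 SD, correlation 0.6, ICC 0.1, 10 people per barangay.

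- Individually randomised n per arm: 2 × (1.96 + 0.842)² / 0.12² ≈ 1,091.
- × (1 − 0.6²) × (1 + 9 × 0.1) = 1,091 × 0.64 × 1.9 = 1,327, against 1,306 in Table 6 (+1.6%).
- The same formula gives 1,012, 1,909, 1,457 and 1,741 for Scenarios 2–5, against 1,000, 1,880, 1,440 and 1,722 in Tables B1–B4.

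The design is therefore understood. Table 6 sets the lottery and control arms at 1,361 each for the binary outcomes, or about 136 barangays of 10.

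**2. What the ratio rule does.** Let k_g be the lottery coefficient in group g. The full-sample coefficient is approximately the share-weighted average of the k_g, so the ratio for R < 0 exceeds 1 when its coefficient exceeds that of everyone else combined. With no true difference, that gap is centred on zero and roughly symmetric, so the rule fires about half the time whatever the sample size. For the largest of three groups, symmetry gives 1/3 when groups are equal in size. The figure is higher when the risk-loving group is small and noisy, and lower when it is large.

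**3. Simulation under no association.** 136 barangays × 10 per arm, beta-binomial attendance with ICC 0.1, three groups assigned independently of response, 2,000 replicates per setting. The documents do not give group shares, control attendance or the ICC of attendance. Assumed: risk-loving share 10–70%, neutral share 2–33%, control attendance 10% or 20%, lottery effect 60, 50 or 20 points (18 settings).

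| Meaning of higher | False support |
|---|---|
| Ratio above 1 | 49–52% |
| Above the risk-averse group | 48–53% |
| Largest of the three groups | 26–40% |
| R < 0 versus the rest, two-sided 5%, hypothesised direction | 1.8–3.1% |
| Same, one-sided 5% | 4.3–5.8% |

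The Monte Carlo standard error near 50% is √(0.25/2,000) ≈ 1.1 points. The last two rows use the simulated standard deviation of the gap as its standard error.

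**4. Size of chance departures within the plan's compliance range.** With equal thirds, the standard deviation of the ratio is 0.036 at a 60-point effect and 0.045 at 50 points. That gives 1 ± 1.96 × SD = 0.93–1.07 and 0.91–1.09. With a 10% risk-loving share and 20% neutral, the SDs are 0.076 and 0.094, giving 0.85–1.15 and 0.82–1.18.

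**5. What a proper test could detect.** The standard error of the gap (R < 0 minus the rest) is 0.031–0.058 across settings. Hand check for a 30% share and attendance of 80% versus 20%: √[2 × 0.16 × (1/408 + 1/952)] = 0.033, matching the simulated 0.033. The gap detectable with 80% power is 2.80 × 0.031 to 2.80 × 0.058, about 9–16 percentage points.

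**The case against.** The strongest reply is that the bullet describes compliers and that the testing has already been done. Model (6.3), the risk-attitude indicators and model (6.4) come first and can all be tested formally. The plan also states many results by sign as shorthand, and elsewhere in [H6c] it does use significance language.

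Much of this stands. A reader might infer that [H6c] as a whole rests on a coin flip; it does not, because the interaction models exist. Four other stronger readings also fail:

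- **[H6d] is decided the same way.** Its text only computes and compares the ratios; no support rule is stated.
- **Repeating over many groups guarantees a supportive one.** Some group will nearly always exceed 1 by arithmetic, but the plan has no rule for picking the largest. It names directions in advance.
- **The ratio is misdefined.** It is a correct relative likelihood. A value above 1 means over-represented among compliers, not a majority of them.
- **Chance ratios will be far from 1.** Very wide ranges need a lottery effect near 20 points, outside the plan's 50–60% compliance.

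Two things remain. The bullet sits under the test heading, states what supports the hypothesis, and does not yield to the interaction test if the two disagree. And (6.4) has no term for the joint α-by-r groups. The plan does compare lottery response across groups that also use perceived risk, again without a criterion. So the bare ratio is the only procedure it calls a test of whether compliers combine convex utility with overweighting of small probabilities.

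**Conclusion.** The concern holds for [H6c]. Read literally, the ratio rule gives nominal support about 50% of the time when risk attitude is unrelated to lottery response, or 26–40% on the largest-of-three reading. The 50% figure follows from symmetry and does not depend on the assumed shares, attendance or effect size; the 26–40% range and the chance intervals do. Noise in the individual risk parameters, which the plan anticipates, would weaken a true difference but would not repair the rule.

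The consequence is limited to a secondary mechanism hypothesis and the description of compliers. A reader might infer that the PhilPEN estimate itself is compromised. It is not: the principal outcome, the estimate from (6.1) and the sample size do not use the ratio.

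**What to change.** In [H6c], state that the ratio counts as support only if the first-stage lottery coefficient for R < 0 exceeds that of the other groups at the 5% level. Either of two near-equivalent routes would serve:

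- the lottery × risk-group interaction already planned, with standard errors clustered on barangay; or
- a 95% interval for the ratio, from resampling barangays, that lies above 1.

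Name the comparator. The planned indicator model uses risk neutral as reference, so a comparison of R < 0 with everyone else has to be written as an explicit contrast. Say whether the test is one- or two-sided. State that the ratio does not override this test.

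Apply the same criterion to the α-by-r combinations, with a joint test of equal lottery response before any one group is singled out. In [H6d], report the relative likelihoods with the same intervals. Reporting each group's share of compliers (ratio × group share) is optional.

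The cost is a few sentences and a contrast or bootstrap on regressions already planned. The downside is fewer nominally supportive profiles: differences smaller than about 9–16 points will often be inconclusive.
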